8.2 Documentation and Reporting of Adverse Events By the Investigator

All adverse events (AEs) occurring after the application of the first dose through the End of study visit/or early termination, will be reported on the AE CRF pages. Based on the medical judgement of the investigator, all non-serious systemic and skin AEs will be followed until 30 days after the final end of study visit. All non-resolved, non-serious systemic and skin AEs beyond such date will be recorded as 'ongoing' without further follow up.

However, an AE form will not be filled out for subjects who sign the ICF but fail the entry criteria (Screening failures) during the Screening process and experience a non-serious AE.

Application site reactions will be reported on a dedicated assessment form for the visual skin assessment of the application sites. The regular AE form does not have to be completed for such events unless the events are not covered by the questions on the visual skin assessment form or are reported outside their time window. However, all such events will be included in the analyses of adverse event incidence.

Each AE, including skin AEs, is to be assessed to determine if it meets the criteria for an SAE. If an SAE occurs, expedited reporting will follow local and international regulations, as appropriate (See [Section 8.4](#)). It should be noted that the form for collection of SAE information is not the same as the AE CRF. Where the same data are collected, the forms must be completed in a consistent manner. For example, the same AE term should be used on both forms. Systemic and skin AEs should be reported using concise medical terminology on the CRF pages as well as on the form for collection of SAE information.

In addition to recording the signs, symptoms or diagnosis associated with them to describe the adverse event, the following will also be assessed and recorded:

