STUDY DURATION	Screening (up to 30 days prior to dosing); in-clinic duration of study participation for each subject is approximately 2 weeks total (includes 4 treatment periods), and the End of Study (or Early Termination) visit occurs on the day of discharge
PROCEDURES & ASSESSMENTS	
All procedures are performed relative to Time 0 (M207 application), the time of second patch application.
 
• Physical examination (Screening, 8 hr post drug administration and End of Study/or Early Termination visit)• Clinical laboratory tests (Screening, and End of Study/or Early Termination visit)• Collection of blood samples (pre-dose, 2, 5, 10, 15, 20, 30, 45, 60, 90 min, 2 hr, 4 hr, 8 hr, 12 hr and 24 hr post-dose) for pharmacokinetics determination• Vital signs (Screening, pre-dose and 10 min, 60 min, 2 hr, 4 hr, 12 hr post-dose and End of study/or Early Termination visit)• 12-lead ECGs (Screening, pre-dose, 15 min, 12 hr post-dose, and End of Study/or Early Termination visit)• Investigator visual skin assessment of the M207 application site at pre-dose, 30 min, 60 min, 8 hr, 24 hr post-dose, and End of Study/or Early termination visit• Residual zolmitriptan swabbing on the skin at 30 min post-dose

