2 STUDY OBJECTIVES

The study objectives are as follows:

To compare the pharmacokinetics, safety and tolerability of M207 3.8 mg Treatment A to M207 3.8 mg Treatment B to M207 3.8 mg Treatment C, each worn for 30 minutes on the upper arm.

To compare the pharmacokinetics, safety and tolerability of these three formulations of M207 3.8 mg to Treatment D intranasal zolmitriptan 2.5 mg.

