4.2 Endpoints

The endpoints of the study are:

Safety and Tolerability

- Incidence of adverse events
- Change in physical exam findings from pre-dose to 8 hr post-dose
- Changes in vital signs from pre-dose to 10 minutes, 60 minutes, and 2, 4 and 12 hr post-dose
- Changes in ECG parameters from pre-dose to 15 minutes and 12 hr post-dose
- Scores from the investigator visual skin assessment for erythema, edema, bruising and bleeding at the patch application sites from pre-dose to 30 minutes, 60 minutes, 8 hr and 24 hr post-dose

Pharmacokinetics

- C_{max} - maximum observed plasma concentrations
- T_{max} - time to maximum concentration
- AUC_{0-last} - the area under the plasma concentration time profile from hour 0 to the last detectable concentration at time t.
- $AUC_{0-30min}$ - the area under the plasma concentration time profile from minute 0 to minute 30.
- $AUC_{0-60min}$ - the area under the plasma concentration time profile from minute 0 to minute 60.
- $AUC_{0-120min}$ - the area under the plasma concentration time profile from minute 0 to minute 120.

- k - apparent elimination rate constant will be estimated by linear regression of the log-transformed plasma concentrations during the terminal log-linear decline phase.
- $t_{1/2}$ - apparent half-life ($t_{1/2}$) values will be calculated as $0.693/k$.
- $AUC_{0-\infty}$ - the AUC value extrapolated to infinity will be calculated as the sum of AUC_t and the area extrapolated to infinity, calculated by the concentration at time t (C_t) divided by k.
- F_{rel} - bioavailability relative to each treatment assignment

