7.3.4 Investigator Visual Skin Assessments of the Application Sites

Each M207 patch site (where a patch has been removed) will be observed for the following skin assessments pre-dose and immediately after removal of the patches from the subject's skin (and before swabbing) at 30 min, 60 min, 8 hr, 24 hr and at the End of Study/or Early Termination visit.

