10.5 Analyses of Safety Data

AEs will be coded using the most current version of Medical Dictionary for Regulatory Activities (MedDRA®) available at Celerion and summarized by treatment for the number of subjects reporting the treatment emergent adverse event (TEAE) and the number of TEAEs reported. A by-subject AE data listing including verbatim term, coded term, treatment, severity, and relationship to treatment will be provided.

Concomitant medications will be listed by subject and coded using the most current version of the World Health Organization (WHO) drug dictionary available at Celerion.

Scores from the investigator skin assessment of the application sites at 30 minutes, 60 minutes, 8 hours and 24 hours post-dose will be summarized by treatment group using frequency tables.

Descriptive summaries of actual values and changes from pre-dose to 10 minutes, 60 minutes, 2 hours, 4 hours, and 12 hours post-dose will be calculated for vital signs including heart rate, respiratory rate, systolic blood pressure, and diastolic blood pressure and presented by treatment group.

Descriptive summaries of actual values and changes from pre-dose to 15 minutes and 12 hours post-dose will also be provided by treatment group for the quantitative ECG parameters of rhythm, heart rate, PR interval, QRS interval, QT, and QTcF (Fridericia's formula correction).

All safety data will be listed by subject and parameter, separate listings of all abnormal laboratory findings will be provided, and clinically significant abnormalities will be recorded as AEs.

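### Section 8.2 counts every patch-site reaction in adverse event incidence, but only M207 has scheduled post-dose local inspections, so overall TEAE incidence for M207 versus nasal spray partly reflects unequal local ascertainment

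*Protocol*

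**What the plan says.** The second objective in Section 2 is "To compare the pharmacokinetics, safety and tolerability of these three formulations of M207 3.8 mg to Treatment D intranasal zolmitriptan 2.5 mg". The first safety endpoint in Section 4.2 is "Incidence of adverse events".

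Section 8.2 records application-site reactions on a dedicated skin form and adds: "However, all such events will be included in the analyses of adverse event incidence". It gives no minimum score. On the erythema scale in Section 7.3.4.1 the lowest non-zero grade is mild redness.

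The inspections that produce these events belong to M207. The synopsis lists "Investigator visual skin assessment of the M207 application site at pre-dose, 30 min, 60 min, 8 hr, 24 hr post-dose", with a further look at End of Study. Section 7.3.4 ties them to patch sites: "Each M207 patch site (where a patch has been removed) will be observed for the following skin assessments pre-dose". The signs scored are erythema, edema, bruising and bleeding.

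For Treatment D the only scheduled local check is a nasal inspection before dosing (Section 6.3.1.1, and one mark in the pre-dose column of the Section 13 schedule). No nasal check is listed at any post-dose time in Sections 6.3.1.3 to 6.3.1.16 or at End of Study in Section 6.4.

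Section 10.5 plans for TEAEs to be "summarized by treatment for the number of subjects reporting the treatment emergent adverse event (TEAE) and the number of TEAEs reported". Separately it plans frequency tables for "Scores from the investigator skin assessment of the application sites at 30 minutes, 60 minutes, 8 hours and 24 hours post-dose".

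**The concern.** Two treatments can be compared on adverse event incidence only if events of the same kind had a similar chance of being found. Here local events at the patch site are looked for on a timetable. Local events in the nose after dosing reach the database only through adverse event recording and the general physical examination. Because Section 8.2 puts every patch-site reaction into the incidence analyses, that difference in looking enters both summary measures in Section 10.5: subjects with a TEAE and number of TEAEs.

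At stake is how the M207-versus-D safety comparison is read. With no formal test planned, readers will rely on the descriptive contrast. A higher overall TEAE figure for M207 could come from worse systemic tolerability, from genuine patch-site reactions, or from closer inspection of the patch site. The overall figure cannot tell these apart.

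**Working it through.** There is no stated figure to reproduce: Section 10.1 reports no formal sample size calculation, and the protocol gives no reaction rates. The check is a count of scheduled inspections, followed by a look at what the planned summaries can recover.

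**Inputs**
- Patch sites per M207 dose: 2 (Section 5.1)
- Scheduled post-dose skin inspections per M207 period: 4 (synopsis, Sections 4.2, 7.3.4 and 10.5)
- Signs scored per site: 4 (Section 7.3.4)
- Subjects: 24; M207 treatments: 3 (Sections 4.4 and 5.1)
- Scheduled post-dose nasal inspections for D: 0

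**Count**
- Per M207 subject-period: 2 × 4 = 8 inspections, and 8 × 4 = 32 scores
- Per M207 treatment: 8 × 24 = 192 inspections
- Over A, B and C: 192 × 3 = 576 inspections
- Treatment D: 0 × 24 = 0

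Cross-check: 24 × 3 × 2 = 144 patch sites, which agrees with the 144 used-patch vials in Appendix 3, and 144 × 4 = 576.

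The 60-minute skin inspection is missing from the visit list in Section 6.3.1.10. If it is not done, the counts become 2 × 3 = 6 per period, 6 × 24 = 144 per treatment and 144 × 3 = 432 overall. The End of Study look is not counted in either version.

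These are opportunities to find an event, not events.

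**Mechanism, with assumed rates only**
Let s be the risk of a systemic TEAE, L the true risk of a local reaction and d the share of local reactions captured. Assuming independence, the chance of any TEAE is 1 − (1 − s)(1 − L·d). Take s = 20% and the same L for both products, with d = 1 for M207 and d between 10% and 50% for D.
- L = 30%, d = 10%: M207 is 1 − 0.8 × 0.7 = 44.0%; D is 1 − 0.8 × 0.97 = 22.4%; gap 21.6 points.
- L = 10%, d = 50%: 28% against 24%; gap 4 points.
- L = 90%, d = 10%: 92% against 27.2%; gap 64.8 points.
- d = 1 for both, or local events left out of both: gap 0.

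None of these rates comes from the protocol, and equal local risk for skin and nose is a simplification. A spread of 4 to 65 points shows how the mechanism works and that its size is open.

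**What the planned tables can recover**
A subject with both a local and another TEAE counts once in the overall figure: n(any) = n(local) + n(non-local) − n(both). The summary rows do not give n(both), so subjects with any non-local TEAE cannot be obtained by subtraction.

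**The case against.** The strongest reply is that nothing is wrong with the data and that table layout belongs in the SAP. Patch-site reactions meet the adverse event definition in Section 8.1, and counting them is proper. Section 10.5 codes events in MedDRA, tabulates skin scores separately, and promises: "A by-subject AE data listing including verbatim term, coded term, treatment, severity, and relationship to treatment will be provided". A reader can therefore tell application-site terms from systemic ones, and with 24 subjects could count by hand. The analysis has no test, and Section 10.1 expects only directional information on tolerability.

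Much of this stands. No error rate is affected, and separation is partly possible already. But the point does not rest on a missing SAP detail. Section 8.2 states a rule, and applied as written it makes any overall M207-versus-D figure depend on unequal inspection. Section 10.5 plans no incidence free of that dependence.

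A reader might also infer that adverse events on Treatment D days are not actively collected. The protocol does not support that. Section 8.1 includes events found by investigator questioning and physical examination. Adverse events are explicitly recorded at 30 and 60 minutes and at 12 and 24 hours. Section 6.3.1 applies the same procedures on all dosing days, including the 8-hour physical examination, and subjects are confined to the clinic. What D lacks is narrower: a dedicated post-dose nasal inspection to match the patch-site inspections. Because the general procedures also run on M207 days, they do not offset the difference.

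**Conclusion.** The concern holds as a limited point about interpretation. Under Section 8.2, an overall TEAE incidence for M207 versus D, whether in subjects or events, partly reflects unequal local ascertainment. The comparison of A, B and C, which Section 1.1 gives as the purpose of the study, is unaffected because all three have the same skin inspections.

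Neither the size nor the net direction of the resulting difference can be derived from the protocol. The 8-to-0 count per subject-period (6 to 0 without the 60-minute check) describes opportunity. It would be tempting to read 576 against 0 as a measure of bias, or to treat an M207 excess as an artefact of inspection. Neither follows: the protocol gives no event rates, and part of any local difference may be a genuine effect of the patch.

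The conclusion assumes that the inspection times in the synopsis and Sections 7.3.4 and 10.5 are followed, and that no nasal inspection is made after dosing beyond what is scheduled.

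**What to change.** Keep site reactions reportable and in the adverse event data. In Section 10.5:

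- Add TEAE incidence by treatment, in subjects and events, excluding local administration-site events: patch-site for M207 and nasal for D. Base the systemic M207-versus-D statement on this table.
- Show local administration-site events separately, with a note that M207 sites had scheduled post-dose inspections and Treatment D did not.
- Show the combined incidence only beside these two.

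The cost is one extra table and a short note. No assessment is added, and the summaries already planned remain. The downside is that there is no longer a single headline TEAE rate.

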8.2.1 Duration

Record the start date and time of the event, and, if applicable, the end date and time. If the event is still ongoing at the final or early termination visit or after the end of follow-up, this should also be recorded.

8.2.2 Severity Ratings

The Investigator will evaluate the severity of each AE using the following definitions:

- Mild - event may be noticeable to patient; does not influence daily activities; usually does not require intervention.
- Moderate - event may be of sufficient severity to make patient uncomfortable; performance of daily activities may be influenced; intervention may be needed.
- Severe - event may cause severe discomfort; usually interferes with daily activities; patient may not be able to continue in the study; treatment or other intervention usually needed.

Note the distinction between the severity and the seriousness of an AE. A severe event is not necessarily an SAE. For example, a headache may be severe (interferes significantly with patient's usual function) but would not be classified as serious unless it met one of the criteria for SAEs, listed above.

8.2.3 Relationship to Study Drug

The Investigator's assessment of causality must be provided for all systemic and skin AEs (serious and non-serious). An Investigator's causality assessment is the determination of whether there exists a reasonable possibility that the investigational product caused or contributed to an AE. If the Investigator's final determination of causality is unknown and the Investigator does not know whether or not the investigational product caused the event, then the event will be handled as "related to investigational product" for reporting purposes. If the Investigator's causality assessment is "unknown but not related to investigational product", this should be clearly documented on study records.

In addition, if the Investigator determines an SAE is associated with study procedures, the Investigator must record this causal relationship in the source documents and CRF, as appropriate, and report such an assessment in accordance with the SAE reporting requirements, if applicable.

After careful medical consideration, the Investigator will evaluate the relationship of each AE to study drug applying the following definitions:

Probably Related: An AE that is likely due to the use of the study drug. The relationship in time may be suggestive. An alternative explanation is less likely, e.g., concomitant drug(s), concurrent disease(s).

Possibly Related: An AE that may or may not be due to the use of the study drug. The relationship in time is reasonable; therefore, a causal relationship cannot be excluded. An alternative explanation is inconclusive, e.g., concomitant drug(s), concurrent disease(s).

Not Related: An AE that is judged to be clearly due only to extraneous causes (disease, environment, etc.). The cause must be noted on the AE CRF page.

8.3 Serious Adverse Event Definitions

A serious adverse event (SAE) or reaction is any untoward medical occurrence that at any dose:

- Results in death;
- Is life-threatening (immediate risk of death);
- Requires inpatient hospitalization or prolongation of existing hospitalization;
- Results in persistent or significant disability/incapacity; or
- Is a congenital anomaly/birth defect.

Important medical events that may not result in death, be life-threatening, or require hospitalization may be considered an SAE when, based upon appropriate medical judgment, they may jeopardize the patient and may require medical or surgical intervention to prevent one of the outcomes listed in this definition.

Definition of disability: A substantial disruption of a person's ability to conduct normal life functions.

Life-threatening SAE: Any AE that places the patient, in the view of the Investigator, at immediate risk of death from the reaction as it occurred (i.e., it does not include a reaction that had it occurred in a more severe form, might have caused death).

Hospitalization: AEs reported from clinical trials associated with hospitalization or prolongation of hospitalization is considered serious. Hospitalization does not include the following:

- Rehabilitation facilities;
- Hospice facilities;
- Respite care (e.g., caregiver relief);
- Skilled nursing facilities;
- Nursing homes;
- Routine emergency department admissions; or
- Same day surgeries (as outpatient/same day/ambulatory procedures).

Hospitalization or prolongation of hospitalization in the absence of a precipitating, clinical AE is not in itself an SAE. Examples include:

- Admission for treatment of a preexisting condition not associated with the development of a new AE or with a worsening of the preexisting condition (e.g., for work-up of persistent pre-treatment lab abnormality);

- Social admission (e.g., patient has no place to sleep);
- Administrative admission (e.g., for yearly PE); or
- Pre-planned treatments or surgical procedures that have been noted in the baseline documentation for the entire protocol and/or for the individual patient.

Pregnancies, though not expected in this subject population, are not reported as SAEs. Pregnancy follow-up should describe the outcome of the pregnancy, including any voluntary or spontaneous termination, details of the birth, the presence or absence of any congenital abnormalities, birth defects, maternal or newborn complications and their relation to the study treatment.

Unexpected Adverse Events

An unexpected AE is any AE, the specificity or severity of which is not consistent with the current Investigator brochure; or if an Investigator brochure is not required or available, the specificity or severity of which is not consistent with the risk information described in the general investigational plan or elsewhere in the current application, as amended. “Unexpected,” as used in this definition, refers to an AE that has not been previously observed (i.e., is not included in the Investigator brochure) rather than an event that is not anticipated based on the pharmacological properties of the pharmaceutical product.

8.4 Reporting Requirements For Serious Adverse Events

ALL SERIOUS ADVERSE EVENTS, REGARDLESS OF CAUSE(S) OR RELATIONSHIP TO STUDY DRUG MUST BE REPORTED IMMEDIATELY TO THE SPONSOR BY TELEPHONE AND FAX.

8.4.1 Sponsor SAE Contact Information

[name], MSc
Phone/[contact]

If an SAE occurs, the Sponsor is to be notified within 24 hours of awareness of the event by the Investigator. In particular, if the SAE is fatal or life-threatening, notification to the Sponsor must be made immediately, irrespective of the extent of available AE information. This timeframe also applies to additional new information (follow-up) on previously forwarded SAE reports.

The Investigator must complete the SAE Report Form and send it along with other relevant source documents to the medical monitor within 24 hours. For all SAEs, the Investigator is obligated to pursue and provide information to the medical monitor in accordance with the timeframes for reporting specified above. The Investigator (or a physician on the investigational staff) must provide relationship to study drug as soon as possible and sign the SAE forms. The Investigator must also provide any relevant information regarding the SAE and respond to requests for follow-up in a timely manner. All SAEs will also be reported on the AE CRF page and CM administered in association with the SAE will be documented on the CRF.

If an SAE occurs and comes to the attention of the Investigator after study termination within 30 days of the last dose of study drug(s), it must be reported immediately to the sponsor in the same way as the SAEs occurring during the study.

8.4.2 Follow up of Adverse Events

All SAEs must be followed up until resolution or, in the Investigator's opinion, a stable condition is reached, or until the patient is lost to follow up. Based on the medical judgment of the Investigator, all non-serious systemic and skin AEs will be followed until 30 days after the last visit. All non-resolved, non-serious systemic and skin AEs beyond such date will be recorded as "ongoing" without further follow up.

9 DATA MANAGEMENT

9.1 Data Collection

Designated investigator staff must enter the information required by the protocol into the study CRF on an ongoing basis. The completed CRF pages will be reviewed against source documents by the monitor at each monitoring visit. If any data, signatures, or forms are missing or incorrect, the Investigator will be informed and corrections made. Celerion standard CRFs will be supplied. CRFs are produced, stored electronically, and are available to the designated study team members. Each CRF is reviewed and signed by the PI. The final signed CRFs are provided to the Sponsor on CD.

